3.3 Inclusion of Women and Minorities

Both men and women and members of all races and ethnic groups are eligible for this trial.

4 REGISTRATION PROCEDURES

Patients must not start any protocol intervention prior to registration through the Siteman Cancer Center.

The following steps must be taken before registering patients to this study:

- 1. Confirmation of patient eligibility
- 2. Registration of patient in the Siteman Cancer Center database
- 3. Assignment of unique patient number (UPN)

4.1 Confirmation of Patient Eligibility

Confirm patient eligibility by collecting the information listed below:

- 1. Registering MD's name
- 2. Patient's race, sex, and DOB
- 3. Three letters (or two letters and a dash) for the patient's initials
- 4. Copy of signed consent form
- 5. Completed eligibility checklist, signed and dated by a member of the study team
- 6. Copy of appropriate source documentation confirming patient eligibility

4.2 Patient Registration in the Siteman Cancer Center OnCore Database

All patients must be registered through the Siteman Cancer Center OnCore database.

4.3 Assignment of UPN

Each patient will be identified with a unique patient number (UPN) for this study. All data will be recorded with this identification number on the appropriate CRFs.

4.4 Screen Failures

Screen failures are defined as participants who consent to participate in the clinical trial but are not subsequently randomized to the study intervention or entered in the study. A minimal set of screen failure information is required to ensure transparent reporting of screen failure participants, to meet the Consolidated Standards of Reporting Trials (CONSORT) publishing requirements and to respond to queries from regulatory authorities. Minimal information includes demography, screen failure details, eligibility criteria, and any serious adverse event (if applicable).

4.5 Strategies for Recruitment and Retention

All patients with pancreatic cancer are discussed in our weekly multidisciplinary tumor board and clinical trial options are reviewed. WUSM department of surgery preforms greater than 100 pancreatic cancer resections per year. Many of these patients would be eligible for this trial. We anticipate an accrual rate of approximately 15 patients per year. To have outreach meetings in the community to explain the radiation therapy and clinical trial options available at Washington University. We will accrue without respect to race, gender or socioeconomic background.

4.6 Measures to Minimize Bias: Randomization

Consenting and eligible patients will be randomized on a 1:1 basis to receive CDX-1140 followed by surgery or CDX-301 + CDX-1140 followed by surgery until 12 patients evaluable for the primary objective have been randomized to each arm. The randomization table will be generated by the statistician using a statistical software and will be uploaded to REDCap to randomize patients.

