3 STUDY POPULATION

3.1 Inclusion Criteria

- 1. Histologically or cytologically confirmed surgically resectable pancreatic ductal adenocarcinoma, but not adenosquamous/squamous pancreas cancers (as determined by operating surgeon or tumor board). Patients who have previously received chemotherapy for his/her pancreas cancer within the past 6 months and who are now deemed resectable are also eligible for this trial.
- 2. At least 18 years of age.
- 3. ECOG performance status ≤ 1 (see Appendix A)
- 4. Normal bone marrow and organ function as defined below:
 - a. Absolute neutrophil count $\geq 1,500$ /cumm
 - b. Platelets > 100,000 /cumm
 - c. Hemoglobin $\geq 9.0 \text{ g/dL}$
 - d. $AST(SGOT)/ALT(SGPT) \le 2.5 \times IULN$
 - e. Creatinine clearance ≤ 1.5 x IULN or glomerular filtration rate of ≥ 60 mL/min
 - f. INR \leq 1.5 x IULN unless patient is receiving anticoagulant therapy as long as INR or PTT is within therapeutic range of intended use of anticoagulants
 - g. $aPTT \le 1.5 \times IULN$ unless patient is receiving anticoagulant therapy as long as INR or PTT is within therapeutic range of intended use of anticoagulants
 - h. Albumin $\geq 3.0 \text{mg/dL}$
- 5. The effects of CDX-301 and CDX-1140 on the developing human fetus are unknown. For this reason, women of childbearing potential and men must agree to use adequate contraception (hormonal or barrier method of birth control, abstinence) prior to study entry, for the duration of study participation, and for 3 months after the last dose of either study drug. Should a woman become pregnant or suspect she is pregnant while participating in this study or for 3 months after the last dose of either study drug, she must inform her treating physician immediately.

6. Ability to understand and willingness to sign an IRB approved written informed consent document (or that of legally authorized representative, if applicable).

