11 MEASUREMENT OF EFFECT

Primary Endpoint: This study is powered to detect a two-fold change in intratumoral conventional dendritic cells between CDX-1140 vs. CDX-301 plus CDX-1140 treated patients. This is a critical endpoint to ensure CDX-301 plus CDX-1140 is having its intended biological effect and thus has a likelihood of impacting tumor immunity and patient outcomes.

Correlative Secondary Endpoints: These will include global immune profiling by CyTOF, single cell RNASeq analysis, and histologic assessments. Critical to this assessment will be comparative analysis of the impact of CDX-1140 vs. CDX-301 plus CDX-1140 on T cell and cDC number and phenotype.

Exploratory endpoints: These will include local control rate, distant metastasis-free survival (DMFS), overall survival (OS), and margin negative resection rate. Proportions of local control and margin negative resection for all treated patients.

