13.2 Sample Size Calculation

The primary endpoint is intratumoral conventional dendritic cells (cDCs) at surgery. The sample size calculation is based on the primary endpoint only. Our pilot data in animal models showed that the mean and standard deviation of the number of intratumoral cDCs per gram of tissue in CD40 agonist IgGs was 44726 with a standard deviation of 37895, and for mice treated with CDX-301 plus CD40 agonist, the mean cDCs per gram of tissue was 2716742 with a standard deviation of 1322448. Assuming a similar therapeutic effect on cDCs and similar distribution among samples, 12 patients per arm will have at least 99.9% power to detect the intratumoral cDCs difference as measured by CyTOF between two arms using a two-sided two-group T-test at the type I error of 5%. We plan to enroll 12 patients evaluable for the primary objective per arm for a total of 24 evaluable patients. An interim analysis can be performed at 5 patients per arm or greater; 5 patients per arm will have >80% power to detect changes in cDCs.

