13.4.4 Endpoint Analysis

The primary endpoint is intratumoral cDCs in surgical tissues. Conventional dendritic cells are defined by the lack of expression of CD3, CD19, CD20, CD16, CD56, and the expression of CD45, CD11c, MHCII high and either CD1c or CD141. Kruskal-Wallis test will be used to compare the difference between two

arms.

Exploratory endpoints include global immune profiling by CyTOF, single cell RNASeq analysis, and histologic assessments. Kruskal-Wallis test will be used to compare the difference on T cell and cDC number and phenotype between two arms.

Additional exploratory endpoints include local control rate, distant metastasis-free survival (DMFS), overall survival (OS), and margin negative resection rate. Proportions of local control and margin negative resection for all treated patients and their associated 95% confidence intervals will be calculated assuming a binomial distribution. Chi-square or Fisher's exact test will be used to compare the difference between two arms.

OS is defined as the time from the date of treatment to the date of death, censored at the last follow-up otherwise. DMFS is defined as the time from treatment to the date of distant metastasis or death, whichever occurs first. The alive patients without distant metastasis is censored at the last follow-up. The Kaplan-Meier method will be used to calculate the probability of OS and DMFS. The log-rank test will be considered to compare the difference of OS and DMFS between two arms.

Data on the toxicity in each arm will be collected for each subject, including frequency, type, and severity of adverse events. All analyses will be conducted using SAS (SAS Institute, Cary, NC) at the two-sided 5% significance level.

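### Prior chemotherapy is left out of both the randomisation and the primary test, which costs power at the two-fold effect if it shifts dendritic cell counts

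*Combined protocol and SAP*

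**What the plan says.** **Population.** Section 3.1 makes eligible "Patients who have previously received chemotherapy for his/her pancreas cancer within the past 6 months" if they are now judged resectable, next to patients with no prior chemotherapy. Section 3.2 excludes chemotherapy in the two weeks before the first dose. No section gives the expected share of pretreated patients.

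**Randomisation.** Section 4.6 is the only description. It gives a 1:1 ratio, a table made by the statistician and loaded into REDCap, and enrolment "until 12 patients evaluable for the primary objective have been randomized to each arm". It mentions no stratification factor and no block size. Section 13.1 repeats only the ratio. Section 5.3 replaces patients who are not evaluable for the primary objective, but says nothing about how replacements are allocated.

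**Analysis.** For the primary endpoint, Section 13.4.4 states that the "Kruskal-Wallis test will be used to compare the difference between two" arms. No adjusted or stratified analysis by prior chemotherapy appears anywhere.

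**Effect size.** Section 13.2 is sized on mouse data: the mean "in CD40 agonist IgGs was 44726 with a standard deviation of 37895", and for the combination "the mean cDCs per gram of tissue was 2716742 with a standard deviation of 1322448". It concludes that "12 patients per arm will have at least 99.9% power to detect the intratumoral cDCs difference". Section 11 names a much smaller target: "This study is powered to detect a two-fold change in intratumoral conventional dendritic cells".

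**The concern.** Prior chemotherapy is a binary factor that must be established to check eligibility, so it is available at randomisation at no extra cost. The primary endpoint is one cDC measurement at surgery, with no pre-treatment tumour value to adjust for.

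If prior chemotherapy changes intratumoral cDCs, leaving it out does two things in a trial of 24 evaluable patients. It adds between-patient variance that the unadjusted test treats as noise, which lowers power. It also lets the arms differ by chance in their pretreated share, which shifts the realised comparison. Both matter most if the true treatment effect is nearer the two-fold change of Section 11 than the mouse effect of Section 13.2.

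**Working it through.** **1. The plan's own power figure.** Difference in means: 2716742 − 44726 = 2672016. Root-mean-square SD: √((37895² + 1322448²)/2) ≈ 935,500. Standardised difference d ≈ 2.86. With 12 per arm the noncentrality is 2.86 × √(12/2) ≈ 7.0, and power exceeds 99.99% by pooled or Welch t-test. The stated 99.9% reproduces. The ratio of means is 2716742/44726 ≈ 61; at that effect the simulated Kruskal-Wallis test also has about 100% power, even with a 4-fold chemotherapy effect.

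**2. Log-scale SD.** If counts are lognormal, log-SD = √ln(1 + CV²).
- CD40 agonist alone: CV = 37895/44726 = 0.847, log-SD = 0.735.
- Combination: CV = 1322448/2716742 = 0.487, log-SD = 0.46.

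These mouse values are the only spread the documents offer, so I use both as a range.

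**3. Power at two-fold with no chemotherapy effect.** Noncentrality is ln 2 × √6 / log-SD: 1.698/0.735 = 2.31 and 1.698/0.46 = 3.69. A log-scale t-test has 60% and 94% power; the simulated Kruskal-Wallis test has about 57-59% and 93-94%.

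**4. What an ignored factor does.** With share p pretreated and a c-fold shift, the variance seen by the unadjusted test is about log-SD² + p(1 − p)(ln c)². At p = 0.5:
- log-SD 0.735: √(0.541 + 0.120) = 0.81 for 2-fold; √(0.541 + 0.302) = 0.92 for 3-fold.
- log-SD 0.46: √(0.213 + 0.120) = 0.58 for 2-fold; √(0.213 + 0.302) = 0.72 for 3-fold.

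**5. Simulated power, two-fold treatment effect, 12 per arm, exactly 12 of 24 pretreated** (3,000 trials per cell, simulation error up to 0.9 points). KW is Kruskal-Wallis; LM is a log-scale linear model with treatment and prior chemotherapy.

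| log-SD | Chemotherapy effect | KW, unstratified (as planned) | LM, unstratified | KW, stratified | LM, stratified |
|---|---|---|---|---|---|
| 0.74 | none | 57% | 57% | 56% | 58% |
| 0.74 | 2-fold | 50% | 59% | 48% | 59% |
| 0.74 | 3-fold | 38% | 56% | 35% | 59% |
| 0.46 | none | 93% | 93% | 93% | 94% |
| 0.46 | 2-fold | 75% | 93% | 82% | 94% |
| 0.46 | 3-fold | 56% | 93% | 56% | 94% |

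If instead 30-50% of patients are pretreated and the number varies from trial to trial, the planned test has 52-41% power (log-SD 0.735) or 82-57% (log-SD 0.46) for 2- to 3-fold chemotherapy effects.

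**6. Type I error.** For the planned design it stays at about 5% (4.6-6.0% across these cells, within simulation error). If the list is stratified but the test stays unadjusted, it falls to 3.0% and 1.3% (log-SD 0.74) or 1.8% and 0.3% (log-SD 0.46) for 2- and 3-fold chemotherapy effects.

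**7. Chance imbalance.** With fixed 12/12 arms and K of 24 pretreated, P(difference ≥ 4) sums C(12,a)·C(12,K − a)/C(24,K) over splits with |2a − K| ≥ 4. For K = 6: 2 × (924 + 9504)/134596 = 15%. For K = 8, 12 and 16: 19%, 22% and 19%. An 8-versus-4 split shifts the arm ratio of geometric means by c^(4/12): 2^(1/3) = 1.26 for a 2-fold effect, 3^(1/3) = 1.44 for 3-fold.

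**The case against.** The strongest objection is that no section says prior chemotherapy alters intratumoral cDCs. The two-week washout in 3.2 carries no immune rationale, and another 3.2 criterion exempts immunosuppression that goes with a chemotherapy regimen. The untreated historical patients in 1.3.3 may simply be patients without study drug. This stands: the chemotherapy effect and the pretreated share are both assumptions, and if the effect is nil nothing is lost. It is also true that power is near 100% at the mouse effect, and that the modest power at two-fold comes mainly from the gap between Sections 11 and 13.2, a separate matter.

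Three stronger readings are tempting and not supported.

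- **Inflated false positives.** Given an 8-versus-4 split and a 1.5- to 3-fold chemotherapy effect, the unadjusted test rejects a true null 6-11% of the time (log-SD 0.735). That rate is conditional on an uncommon split. Averaged over the randomisation, the error is about 5%.
- **Forced final assignments.** A reader might infer that the fuller arm closes at 12 and late patients go to the other. Section 4.6 does not say so; its wording equally allows enrolment past 24. An unblocked list with neither arm closed would need a mean of 27.9 evaluable patients, which is overshoot and not bias.
- **No blocking.** Section 4.6 is silent on blocks. The statistician's table may well be blocked.

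Section 13.4.3 summarises baseline characteristics by arm, so an imbalance could be displayed if prior chemotherapy is among them. Displaying it does not restore power.

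**Conclusion.** The point holds as a cheap improvement to precision and balance, not as a flaw that invalidates the test. The gain depends on an effect that the documents do not quantify. At the two-fold target, for a 2- to 3-fold chemotherapy effect with 30-50% pretreated, the planned analysis gives up roughly 8 to 19 points of power at log-SD 0.735 (60% against 52%; 60% against 41%) and 12 to 37 points at log-SD 0.46 (94% against 82%; 94% against 57%). Most of that comes back through adjustment alone, even on an unstratified list. Stratification adds the balance, removing most of the 15-22% chance of a difference of four or more; replacement of non-evaluable patients means it cannot guarantee balance among those analysed. The figures assume lognormal counts, the mouse spreads and no interaction between chemotherapy and treatment.

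**What to change.** **Section 4.6.** For future patients, stratify the REDCap list by prior chemotherapy (yes/no) as the only factor, in permuted blocks of varying, concealed size. Fixed small blocks would be guessable in an open-label, single-site trial. State that a replacement takes the next slot on the same list, that this continues until both arms have at least 12 evaluable, that no patient is assigned to an arm because it lags, and that all evaluable patients are analysed.

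**Section 13.4.4.** Adjust the primary comparison for prior chemotherapy, preferably with a linear model for log cDC count containing treatment and prior chemotherapy, and say how a zero count is handled. If a rank test is wanted, use van Elteren's stratified test.

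Make both changes together: stratifying while keeping the unadjusted test makes it conservative (type I error roughly 0.3-4% for 2- to 3-fold chemotherapy effects).

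**Cost.** A new list and a few sentences. If chemotherapy has no effect, the adjusted log-scale model on a stratified list loses essentially nothing, the same model on the existing list about 1 point of power, and van Elteren about 2-5 points. An arm may slightly exceed 12. If accrual is advanced, change the analysis only.

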5 TREATMENT PLAN

5.1 Premedication Administration

5.1.1 CDX-1140

Prophylactic premedication is required for all patients: diphenhydramine 25/50 mg (or equivalent anti-histamine), 500 to 750 mg paracetamol (acetaminophen), and naproxen sodium 250 mg (or equivalent NSAID) at least 30 minutes prior to CDX-1140 administrations. Ranitidine 150 mg (or equivalent) may also be incorporated into the premedication regimen. Prophylactic premedication with corticosteroids

is to be avoided because of the potential to attenuate the anti-tumor activity of CDX-1140.

CDX-1140 will be administered intravenously over 90 minutes using a 0.22 micron in-line filter.

CDX-1140 post-infusion medication is also required for all patients. In the 24-48 hours following the CDX-1140 infusion, alternate oral acetaminophen (1000 mg) and non-steroidal anti-inflammatory (e.g., ibuprofen 200 mg) q6H. An anti-histamine and anti-emetic may also be utilized if clinically indicated. Patients should be evaluated to determine if continuation of post-infusion medication is needed on the day after CDX-1140 dosing. Note that the potential for toxicity with these drugs and appropriate precaution should be utilized in patients with risk factors for toxicity, e.g. patients with peptic ulcers, increased LFTs, or increased creatinine. Also, care should be taken to medicate for no longer than is necessary in order to avoid potential confounding factors in determining adverse event causality (e.g. increased LFTs).

All patients should be monitored for 4 to 6 hours post administration of CDX-1140 with standard post-infusion monitoring.

5.1.2 CDX-301

Injection site reactions have been infrequent and mild with CDX-301. Premedication with diphenhydramine has been reported to be effective in the prevention of pruritic and erythemic reactions and may be considered for subjects who experience local reactions after treatment with CDX-301. Injection site reactions may also be treated with analgesics (i.e., Tylenol). If there is injection site pain, a numbing cream such as Emla cream can be used prior to administration of CDX-301.

5.2 Study Intervention Administration

Patients randomized to the CDX-1140 monotherapy arm will receive a single IV infusion at a dose of 1.5 mg/kg, with surgery to follow 7-12 days after administration of CDX-1140.

Patients randomized to the CDX-301 + CDX-1140 arm will receive CDX-301 at 75 mcg/kg/day as a subcutaneous injection every day for 5 days (Days 1-5) with CDX-1140 IV at 1.5 mg/kg on Day 8. Patients will be required to be present in clinic for each injection. Surgery will be 7-12 days after administration of CDX-1140.

5.3 Definitions of Evaluability

Patients must undergo collection of blood and tissue at the time of resection in order to be evaluable for the primary objective of determining amount of intratumor cDC. Patients who are not evaluable for the primary objective will not count towards analysis of this

objective and will be replaced. However, these patients will continue on study/in followup to be followed for toxicity and local control, DMFS, and OS regardless of whether they had resection.

All patients who receive any study treatment are evaluable for the exploratory objective of safety and tolerability. Patients are evaluated from first receiving study treatment until time of resection, or until 60 days after end of treatment if resection doesn't take place.

In order to be evaluable for the exploratory objective evaluating immunologic correlates, patients must have blood and tissue collected before and after therapy.

In order to be evaluable for the exploratory objectives of assessing local control, DMFS, and OS, patients must have received at least one dose of study treatment.

In order to be evaluable for the exploratory objective of assessing extent of resection, patient must have received at least one dose of study treatment and undergone resection.

5.4 Concomitant Therapy and Supportive Care Guidelines

The investigational drugs are not known or predicted to interact with other drugs, and are not broken down by CYP enzymes.

Infusion reactions may occur when giving any IV medication. Recommendations for the management of peri-infusional reactions are provided below and may be modified based on local treatment standards and guidelines, as appropriate. Infusion reactions should be graded according to NCI-CTCAE guidelines, http://ctep.cancer.gov. Obtain serum at the time of an infusion reaction.

For Grade 1 symptoms: (Mild transient reaction; infusion interruption not indicated; intervention not indicated)

Remain at bedside and monitor patient until recovery from symptoms.

For Grade 2 symptoms: (infusion interruption indicated but responds promptly to symptomatic treatment [e.g., antihistamines, nonsteroidal anti-inflammatory drugs, narcotics, corticosteroids, i.v. fluids]; prophylactic medications indicated for \leq 24 hours)

Stop the CDX-1140 infusion, begin an i.v. infusion of normal saline, and treat the patient with diphenhydramine 50 mg i.v. (or equivalent) and/or 500 to 1000 mg paracetamol/acetaminophen; remain at bedside and monitor patient until resolution of symptoms. Corticosteroid therapy may also be administered as appropriate. If the infusion is interrupted, then restart the infusion at 50% of the original infusion rate when symptoms resolve; if no further complications ensue after 30 minutes, the rate may be increased to 100% of the original infusion rate. Monitor patient closely. If symptoms recur then no further CDX-1140 will be administered at that visit. The amount of study drug infused must be recorded on the case report form (CRF). Patients who experience an adverse event,

including an infusion reaction of Grade 2, during the 4-6 hour observation period that does not resolve during this time should be observed for 24 hours or until the adverse event resolves with vital sign measurements every 4 hours and additional evaluations as medically indicated for the management of the adverse event.

For Grade 3 or Grade 4 symptoms: (Grade 3: prolonged [i.e., not rapidly responsive to symptomatic medication and/or brief interruption of infusion]; recurrence of symptoms following initial improvement; hospitalization indicated for other clinical sequelae [e.g., renal impairment, pulmonary infiltrates]. Grade 4: life-threatening consequences; urgent intervention indicated).

Immediately discontinue infusion of CDX-1140. Begin an i.v. infusion of normal saline, and treat the patient as follows: Recommend bronchodilators, epinephrine 0.2 to 1 mg of a 1:1,000 solution for subcutaneous administration or 0.1 to 0.25 mg of a 1:10,000 solution injected slowly for i.v. administration, and/or diphenhydramine 50 mg i.v. with methylprednisolone 100 mg i.v. (or equivalent), as needed. Patient should be monitored until the Investigator is comfortable that the symptoms will not recur. Investigators should follow their institutional guidelines for the treatment of anaphylaxis. Patients who experience an infusion reaction of Grade ≥ 3, regardless of resolution, will be observed for 24 additional hours or until the adverse event resolves with vital sign measurements every 4 hours and additional evaluations as medically indicated for the management of the adverse event. In the case of late-occurring hypersensitivity symptoms (e.g., appearance of a localized or generalized pruritus within 1 week after treatment), symptomatic treatment may be given (e.g., oral antihistamine, or corticosteroids). CDX-1140 will be permanently discontinued for patients with Grade 4 infusion reactions or Grade 3 infusion reactions lasting more than 6 hours.

